2.2 Secondary Objectives (or Aim)

The secondary objective is to assess the post-operative correction of the scoliotic curve, as measured by Cobb Angle on Coronal (AP/PA) radiograph of the spine.

3 INVESTIGATIONAL PLAN

3.1 General Schema of Study Design

3.1.1 Screening Phase

Subjects will be screened from patients presenting to the orthopedic clinic for routine clinical care. Patients who satisfy the inclusion and exclusion criteria will be approached and presented information about the clinical study. Those subjects and families who are interested in pursuing the clinical study will be enrolled by providing informed consent/assent. Subjects who learn about the study through social media and contact Nemours for additional information will be directed to have a scoliosis clinical appointment. After that they will follow the same research procedure as the subjects who present in the orthopedic clinic for scoliosis care. This phase will last 1 day

3.1.2 Study Intervention (Surgery)

Enrolled patients who have completed the pre-operative course for anterior spine surgery (Pre-operative SOC and Pre-operative study procedures) will undergo the study intervention comprising implantation of anterior vertebral body screws and PET cord under general anesthesia. This phase will last 1 day (day of surgery). This surgical episode is estimated to last about 5.5 hours; 2.5 hours of anesthesia induction and preparation, 2.5 hours of surgery, and 30 minutes of emergence from anesthesia.

3.1.3 Post-operative follow-up

The Post-operative follow-up phase of the study will last approximately 90 days, beginning with the day after the surgical intervention. This period has 2 set time points for follow-up, which will occur during standard-of-care clinical follow-up visits for spine patients receiving surgical intervention. The two time-points are a POD-45 clinical visit, and a POD-90 clinical visit. During these two clinical visits physical exams, radiographs, and AE / SAE data will be collected. POD 2-44 will be monitored for known complications and AE / SAEs only, as there will be no clinical outcomes data to collect during this time. This data will be abstracted from the medical records. In addition, the patient will be under SOC post-operative care for patients who have undergone Anterior Spinal Surgery. Data from any SOC interventions will also be abstracted from the medical record.

3.2 Allocation to Treatment Groups and Blinding

The study will not be blinded, as the patient must make an informed decision to undergo the intervention, and the surgeon must perform the intervention. Introduction of a sham or placebo group would be impractical and unethical in this context. The study will only enroll one cohort-the Anterior Tethering (Intervention) cohort.

3.3 Study Duration, Enrollment and Number of Sites

3.3.1 Duration of Study Participation

The subject will be followed for at least 10 visits over a 5-year (1825 day) period: 1 day for recruitment /consent, 1 day for the study intervention (surgery), 1 day for each visit: POD45, POD90, POD180, POD365, POD730, POD1095, POD1460, and POD1825. These visits follow the schedule for a patient's standard-of-care follow-up for anterior spinal surgery. Any off-study

visits within the study window will not be captured, unless they are related to an AE / SAE. There is a three-week grace period for post-operative study visits, and a 90 day grace period for extended follow-up visits, making the maximum study participation time 1825 + 90 days after the day of surgery.

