- 5. Associated syndrome, including Marfan Disease or Neurofibromatosis
- 6. Sanders bone age greater than 4
- 7. Thoracic curve less than 35 degrees
- 8. Lumbar curve greater than or equal to 35 degrees
- 9. Unable or unwilling to firmly commit to returning for required follow-up visits
- 10. Investigator judgement that the subject/family may not be a candidate for the intervention

Number Of Subjects

Study Duration

Study Phases:

Screening

Study Treatment

Post-op Follow-Up

The study will be conducted at The Nemours – Alfred I duPont hospital for Children, Division of Orthopedics. Subject inclusion will be based on interest of patients that satisfy the inclusion/exclusion criteria that present to the Orthopedic Clinic. The total study enrollment will be 30 subjects. In the retrospective arm we will aim to enroll all patients who had the tether surgery in the past. The study ends when all patients reach skeletal maturity. Each subject's active participation will last about 5 years after surgery. The entire study is expected to last at least 8 years.

- 1. Screening phase: Subjects will be screened by study staff during a clinical visit in the Orthopedics department. Eligible subjects will be approached and if interested, enrolled during a routine clinical exam.
- 2. Study Treatment: The subject will undergo surgical intervention using accepted standard-of-care anterior approach using the Globus Medical Inc. CreoTM Stabilization System. Vertebral body tethering using screws and Polyethylene Terepthalate cord (Globus Medical, Inc. Reflect/TransitionTM Stabilization System) is investigational.
- 3. Post-operative Follow-up: Subjects will be followed at regular time points at 45 and 90 days post-op during the post-operative phase. Patients will also be seen at visits 180, 365, 730, 1095, 1460, 1825 days post-op during the extended follow-up phase.

Efficacy Evaluations

The primary efficacy evaluation measurement is thoracic Cobb angle (to nearest degree) at the pre-operative visit to Cobb angle during follow-up, especially at two years post-op (POD 730).

Safety Evaluations

We will use phase-specific endpoints to measure safety: 1) Study treatment phase: Any individual-level intraoperative events including neuromonitoring events (loss or change in neurological signaling or function), unanticipated events during surgery, and SAEs.

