3.3.2 Total Number of Study Sites/Total Number of Subjects Projected

The study will be conducted at Nemours – Alfred I duPont Hospital for Children. As this is a registry of an approved device being used in an off-label method, we do not have a maximum number of patients or target enrollment. Based on a broad review of patient visits over the past year, we may expect to enroll up to 15 patients per year. These patients will be followed up clinically until skeletal maturity. The total number of enrolled subjects in both retrospective and prospective arms will be 30.

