3.4 Study Population

3.4.1 Inclusion Criteria

- 1) Males or females age 8 to 16 years old at time of enrollment (inclusive)
- 2) Diagnosis of Idiopathic Scoliosis
- 3) Sanders bone age of less than or equal to 4
- 4) Thoracic curve of greater than or equal to 35 degrees, but no bigger than 60 degrees
- 5) Lumbar curve less than 35 degrees
- 6) Spina bifida occulta is permitted
- 7) Spondylolysis or Spondylolisthesis is permitted, as long as it is non-operative, the patient has not had any previous surgery for this, and no surgery is planned in the future
- 8) Completed standard-of-care procedures as outlined in Section 5
- 9) Subject consent and (if applicable) assent

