5.3 Efficacy Evaluation

The mode of efficacy evaluation for this procedure will be measurement of Cobb Angle. Cobb Angle is a coronal plane radiographic measurement of curvature of the spine. This angle will be recorded for the pre-operative coronal spine radiograph, as well as all subsequent serial radiographs. The change in Cobb angle (reduction) will be the primary evaluator of efficacy. 'Overall study success' of the intervention will be defined by a final Cobb angle of less than or equal to 50 degrees by the time subject reaches skeletal maturity.

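### Section 3.3.1 caps participation at 1825 + 90 days, but overall study success is judged at skeletal maturity, so a subject still immature at about 5.2 years has no defined success outcome

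*Combined protocol and SAP*

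**What the plan says.** On duration, section 3.3.1 states "The subject will be followed for at least 10 visits over a 5-year (1825 day) period", with the last visit at POD 1825. It then allows "a 90 day grace period for extended follow-up visits", "making the maximum study participation time 1825 + 90 days after the day of surgery". Section 4.4.6 (POD 1825) is the last visit listed in section 4. The recording plan for AEs and SAEs in section 8 also closes its extended follow-up phase at POD 1825.

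On the outcome, section 5.3 says that overall study success "will be defined by a final Cobb angle of less than or equal to 50 degrees by the time subject reaches skeletal maturity".

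Two other places point beyond the cap. The synopsis says "The study ends when all patients reach skeletal maturity", although the same paragraph gives about five years of active participation per subject and at least eight years for the whole study. Section 3.3.2 says "These patients will be followed up clinically until skeletal maturity".

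Section 3.4.1 admits ages 8 to 16 and requires Sanders bone age 4 or less. Section 5 labels Sanders 7 as skeletal maturity. The documents give no age at which it is reached. They also have no rule for a subject who is still immature at the last visit.

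**The concern.** A fixed maximum and an outcome defined by maturity can both be honoured only if every subject matures within the maximum. Nothing in the eligibility criteria or visit plan ensures this. The cohort is selected to be immature, and the lower age limit is 8. Section 3.4.1 itself accepts that a child can be at Sanders 4 or below at ages up to 16.

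At stake is the only success criterion that the protocol states. For a subject immature at exit, the analyst has no final angle and no instruction. Two analysts could exclude that subject, score the last available angle, or count a failure, and each could claim to follow the protocol.

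The same mismatch touches one safety definition. Section 6.6.2 counts tether failure as an SAE only if it is noted before maturity, so that risk period runs to maturity, while planned recording stops at POD 1825.

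**Working it through.** **The plan's own figures.** Visits: 1 consent + 1 surgery + 8 post-operative = 10, as stated in section 3.3.1. Maximum time: 1825 + 90 = 1915 days, and 1915 / 365.25 = 5.24 years.

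**Age at exit** = age at surgery + 5.24, taking age at enrollment as age at surgery. Entry at 8.0 gives 13.24, at 9.0 gives 14.24, at 10.0 gives 15.24 and at 11.0 gives 16.24.

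**Who would exit immature.** The age at maturity is an assumption, so a range is shown. Entry-age cut-off = assumed maturity age - 5.24. Shortfall for an entrant aged 8.0 = (assumed maturity age - 8) - 5.24.

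| Assumed age at maturity | Entrants affected | Shortfall for entry at 8.0 |
|---|---|---|
| 13 | none | none |
| 14 | below 8.76 | 0.76 years |
| 15 | below 9.76 | 1.76 years |
| 16 | below 10.76 | 2.76 years |

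These cut-offs use the full 90-day window. A subject seen exactly on day 1825 has 90 / 365.25 = 0.25 years less, so each cut-off rises by about a quarter of a year.

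**Whole-study duration.** At the stated maximum of 15 per year, 30 subjects take 30 / 15 = 2 years to enrol. The last capped exit is then at 2 + 5.24 = 7.24 years, inside the synopsis figure of at least eight. If a child aged 8.0 enrolled at year 2 were followed to an assumed maturity age of 14, 15 or 16, the study would run 8, 9 or 10 years. The synopsis wording allows that; the 1915-day maximum does not.

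**Effect on the success proportion.** With k of 30 subjects unresolved, the gap between scoring all of them as failures and all as successes is k / 30. This is 3.3 percentage points for k = 1, 10 for k = 3 and 20 for k = 6. These values of k are illustrations, not estimates.

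**The case against.** The strongest reply is that the duration statements can be read together: about five years of active visits, then passive clinical follow-up until maturity. The synopsis pairs the two ideas in one paragraph, and section 3.3.1 speaks of a minimum number of visits. This reading is reasonable, and it makes the defect one of alignment. It does not remove the defect. Section 3.3.1 calls its figure a maximum, and no text says that data from later clinical follow-up enter the study. Section 4.6 adds only that serious, related events will be recorded if the investigator becomes aware of them after a subject completes or withdraws. That does not supply a Cobb angle or a maturity reading.

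A second reply is that the consequence is limited, and this stands in full. The primary endpoint is the AE/SAE rate (6.1). The secondary endpoint is change in Cobb angle (6.2, 6.3.3), which the synopsis emphasises at two years, and the synopsis counts progression beyond 50 degrees at five years. All can be observed under the cap. Overall study success has no analysis in section 6.

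A reader might infer that the success proportion is biased upward, because the protocol's Table 3 projects 100% progression for a 35-degree curve at stages 1 to 3. The documents do not support that step. The projection is used to describe curves without a tether. The rationale in 1.1.1 and 1.3.2 is that growth under a tether changes alignment, and 9.3.2.1 lists overcorrection, failure of correction and progression as device risks. Remaining growth could move the angle either way. Nothing says that a pre-maturity angle will be taken as final. If an angle at or below 50 degrees were scored that way, a later rise past 50 would be missed, and for those subjects the error could only raise the proportion. That is conditional on a rule the plan does not contain.

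**Conclusion.** The mismatch holds on the text alone: a 5.24-year maximum with no later data capture, against a success criterion set at skeletal maturity. Any subject immature at exit has no defined success outcome.

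The number affected cannot be fixed from the documents. It ranges from none (maturity at 13) to all entrants below about 10.8 years (maturity at 16), within the ages tried. A reader might infer that the youngest subjects certainly leave too early, or that a particular share of the 30 is lost. Neither follows. With entry ages spread evenly over 8 to 16, the shares for maturity at 14, 15 and 16 would be 0.76/8, 1.76/8 and 2.76/8, or about 9.5%, 22% and 35%. Spread evenly over 10 to 14, they would be 0%, 0% and 0.76/4 = 19%. The documents support neither spread. The 30 also include retrospective subjects, and the documents do not say how the visit schedule applies to them.

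The direction of any bias is unknown. The section 6 endpoints and the five-year progression count are not affected. The tether-failure SAE definition is. The point merits correction because the only stated success criterion may be unobservable for some subjects and the remedy is cheap.

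**What to change.** Reconcile the synopsis, 3.3.1, 3.3.2, 5.3 and the AE/SAE recording plan in section 8, so that they give one end of follow-up and one end of data capture. Align the tether-failure definition in 6.6.2 with the result.

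For subjects not mature on the POD 1825 hand film, allow abstraction of spine films and maturity information already obtained in the clinical follow-up promised in 3.3.2, with no added research radiographs. Hand films may not exist after that point. Section 5 lists the hand x-ray under the new visit but not under standard follow-up visits, and the post-operative hand films in section 4 run only from POD 365 to POD 1825.

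Report overall study success with subjects not shown to be mature listed separately as not yet evaluable, never as successes. Restricting the proportion to mature subjects would itself select against late maturers. Give best-case and worst-case bounds over all treated subjects beside it, counting the unresolved first as successes and then as failures.

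The cost is amendment wording, a few more record abstractions and a less complete success proportion. Immature subjects can be identified from the bone-age readings already scheduled.

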3.3.2 Total Number of Study Sites/Total Number of Subjects Projected

The study will be conducted at Nemours – Alfred I duPont Hospital for Children. As this is a registry of an approved device being used in an off-label method, we do not have a maximum number of patients or target enrollment. Based on a broad review of patient visits over the past year, we may expect to enroll up to 15 patients per year. These patients will be followed up clinically until skeletal maturity. The total number of enrolled subjects in both retrospective and prospective arms will be 30.

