moderate scoliosis in patients with remaining growth is to utilize a thoracolumbosacral orthosis (TLSO brace) to prevent progression of deformity. The scientific evidence has supported the efficacy of this intervention in avoiding progression of the Cobb angle to 50 degrees or more.

If treated with a TLSO brace, many idiopathic scoliosis patients would conceivably be subjected to years of brace wear and the cost and psychological factors inherent therein. Additional downsides of brace treatment include the potentially negative psychosocial impact of wearing an external sign of deformity during adolescence, a key period of emotional development. Prior research has identified negative psychosocial effects related to wearing a brace in children.

Recent evidence has suggested that certain curve patterns will likely progress to 50 degrees or more, despite treatment with a TLSO brace. Sanders, et al. demonstrated a correlation of Cobb angle (greater than 35 degrees) and skeletal maturity (bone age 4 or less) to the risk of progression to 50 degrees or more, despite TLSO bracing. The evidence supports that the current practice of TLSO bracing is not an effective treatment to avoid progression to 50 degrees in these patients. It is on this population (thoracic Cobb angle greater than 35 degrees, bone age of 4 or less) that we intend to test the safety and efficacy of Anterior Vertebral Body Tethering to avoid curve progression to more than 50 degrees.

Objectives:

The objectives of this study are to assess the safety and efficacy of Anterior Vertebral Body Tethering Surgery (AVBT) to treat Idiopathic Scoliosis.

Study Design:

This is a Phase II, non-randomized, open label study of the anterior insertion of a Polyethylene Terephthalate (PET) cord in pediatric scoliosis. The study will be conducted at a single site-Nemours – Alfred I duPont hospital for Children

Setting/Participants:

This is a single-site, Sponsor-Investigator led phase II clinical trial of Vertebral Body Tethering for pediatric idiopathic scoliosis in children aged 8-16 years. The study will have a retrospective arm to collect data from patients who had the tether surgery prior to approval of the prospective study.

Study Interventions and Measures:

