The study intervention is surgical orthopedic implantation of Anterior Vertebral Body Screws with PET cord, by way of thoracoscopic surgery under general anesthesia. The primary outcome measures include assessments of safety of the insertion procedure and of the device, as well as the secondary measure of efficacy by determining the improvement in the angle of deformity. Monitoring will be conducted by a data safety committee, who has extensive training and experience in surgical procedures.

PROTOCOL SYNOPSIS

Study Title

Safety and efficacy of a vertebral body tethering technique for

pediatric idiopathic scoliosis

Funder

Departmental Funds

Clinical Phase

Phase II

Study Rationale

Anterior surgical approach and instrumentation is an accepted standard treatment for idiopathic scoliosis (IS). This study will assess whether the intervention (Anterior Vertebral Tethering) is a safe and efficacious method of anterior approach surgery for spinal deformity in pediatric scoliosis.

Study Objective(s)

Primary

To determine the safety of Anterior Vertebral Tethering surgery

Secondary

To determine the efficacy of Anterior Vertebral Tethering

Test Article(s)

Globus Medical Inc.

Reflect/TransitionTM Stabilization System Polyethylene terephthalate (PET) cord

Study Design

This is a single center prospective, open-label pediatric clinical device trial with a single surgical intervention with retrospective arm to collect data from patients who already had AVT surgery.

Subject Population Key criteria for Inclusion and Exclusion:

Inclusion Criteria

- 1. Males or females age 8 to 16 years old at time of enrollment (inclusive)
- 2. Diagnosis of Idiopathic Scoliosis
- 3. Sanders bone age of less than or equal to 4
- 4. Thoracic curve of greater than or equal to 35 degrees but not larger than 60 degrees
- 5. Lumbar curve less than 35 degrees
- 6. Spina bifida occulta is permitted
- 7. Spondylolysis or Spondylolisthesis is permitted, as long as it is non-operative, the patient has not had any previous surgery for this, and no surgery is planned in the future
- 8. Completed standard-of-care procedures as outlined in Section 5

Subject Population Key criteria for Inclusion and Exclusion:

Exclusion Criteria

- 1. Pregnancy (current)
- 2. Prior spinal or chest surgery
- 3. MRI abnormalities (including syrinx >4mm, Chiari malformation, or tethered cord)
- 4. Neuromuscular, thoracogenic, cardiogenic scoliosis, or any other non-idiopathic scoliosis

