3.4.2 Exclusion Criteria

- 1) Pregnancy (current)
- 2) Prior spinal or chest surgery
- 3) MRI abnormalities (could include syrinx >4mm, Chiari malformation, or tethered cord)
- 4) Neuromuscular, thoracogenic, cardiogenic scoliosis, or any other non-idiopathic scoliosis
- 5) Associated syndrome, including Marfan Disease or Neurofibromatosis
- 6) Sanders bone age greater than 4
- 7) Thoracic curve less than 35 degrees
- 8) Lumbar curve greater than or equal to 35 degrees

- 9) Unable or unwilling to firmly commit to returning for required follow-up visits
- 10) Investigator judgement that the subject/family may not be a candidate for the intervention

Subjects that do not meet all of the enrollment criteria may not be enrolled. Any violations of these criteria must be reported in accordance with IRB Policies and Procedures.

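### As written, the entry criteria exclude the whole planned retrospective arm, and the primary AE/SAE rate pools both arms with no display by arm

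*Combined protocol and SAP*

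**What the plan says.** **The retrospective arm.** The Abstract (Setting/Participants) states: "The study will have a retrospective arm to collect data from patients who had the tether surgery prior to approval of the prospective study". The Synopsis (Study Design) describes a prospective trial "with retrospective arm to collect data from patients who already had AVT surgery". By contrast, Section 3.2 describes a single intervention cohort.

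**Eligibility.** There is one list of criteria, in Sections 3.4.1 and 3.4.2 and repeated in the Synopsis. Inclusion 1 is "Males or females age 8 to 16 years old at time of enrollment (inclusive". Exclusion 2 is "Prior spinal or chest surgery", with no exception. Sanders stage and curve size carry no time anchor. Section 3.4.2 closes by barring anyone who does not meet every criterion and by making violations reportable under IRB policy.

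**Enrollment.** Section 3.3.2 says "we do not have a maximum number of patients or target enrollment" and, a few lines later, "The total number of enrolled subjects in both retrospective and prospective arms will be 30". The Synopsis (Number Of Subjects) says "The total study enrollment will be 30 subjects" and then "In the retrospective arm we will aim to enroll all patients who had the tether surgery in the past". Neither place gives a number for either arm.

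**Analysis.** Section 6.1 makes the rate of AEs/SAEs the primary endpoint. Section 6.3.2 starts every subject's safety analysis on the day of surgery and tabulates AEs by type, body system, severity and relationship. It attaches exact two-sided 95% binomial intervals to device-related AE incidence. Section 6.3.3 analyzes Cobb change in all operated subjects. Section 6 does not mention the retrospective arm.

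**The concern.** Two things are at stake.

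The first is whether the retrospective arm can be enrolled under the protocol's own rules. Vertebral body tethering is itself thoracoscopic spinal surgery (Section 1.2.1). Everyone in that arm has therefore had the kind of operation that exclusion 2 names.

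The second is whether the primary endpoint can be read. It would combine two groups whose events were collected under different conditions. Prospective subjects are encouraged to report concerns (the AE/SAE recording plan in Section 8), have complications reviewed at scheduled research visits (Sections 4.3 and 4.4), and are asked at follow-up about care sought between visits (Section 8.9). Patients operated on before the prospective study was approved could not have had this from the day of surgery. A single pooled rate does not let a reader see whether that matters.

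**Working it through.** **1. Eligibility, text against text.**
- The retrospective arm consists only of patients whose tether surgery is already done (Abstract, Synopsis).
- Exclusion 2 has no exception for that surgery, and Section 3.4.2 requires every criterion to be met. Applied at enrollment, it excludes the whole arm.
- Now suppose exclusion 2 were excepted. Age is still fixed at enrollment, with an upper bound of 16. A patient who was 16 at surgery and is enrolled after turning 17 (16 + 1) would fail although eligible when operated on. The interval from surgery to enrollment is not given, so the number affected is unknown.
- Sanders stage and curve size have no anchor. If they too were read at enrollment, a patient who had matured past stage 4, or whose curve had been corrected below 35 degrees, would fail.
- The day-of-surgery anchor in Section 6.3.2 sets the start of the safety analysis. It does not govern eligibility.

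**2. Enrollment.** The stated total is 30. It cannot be re-derived, because Section 6.4 gives no effect size, power or target precision; it is not disputed here. Let R be the number of retrospective patients (not stated). Prospective n = 30 − R, so the aim of taking all past patients decides how many prospective subjects there will be.

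**3. What by-arm display would look like.** This uses the plan's own interval method, the exact two-sided 95% binomial. With 0 events in n subjects the upper limit is 1 − 0.025^(1/n). For x events the limits are the Clopper-Pearson beta quantiles: lower Beta(0.025; x, n − x + 1), upper Beta(0.975; x + 1, n − x). The splits and the 20% observed rate are assumptions for illustration.

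| n | Upper limit, 0 events | 95% interval at 20% observed |
|---|---|---|
| 30 (pooled) | 11.6% | 6/30: 7.7% to 38.6% |
| 20 | 16.8% | 4/20: 5.7% to 43.7% |
| 15 | 21.8% | 3/15: 4.3% to 48.1% |
| 10 | 30.8% | 2/10: 2.5% to 55.6% |

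**4. Could the arms be compared formally?** Assume true rates of 20% and 40%, a two-sided 5% level and the normal approximation, power = Φ[(|p1 − p2| − 1.96·SE0)/SE1], with SE0 from the pooled rate and SE1 from the separate rates.
- 15 v 15: SE0 = √(0.3 × 0.7 × 2/15) = 0.167; SE1 = √(0.16/15 + 0.24/15) = 0.163; power about 22%.
- 10 (at 20%) v 20 (at 40%): SE0 = √(1/3 × 2/3 × (1/10 + 1/20)) = 0.183; SE1 = √(0.16/10 + 0.24/20) = 0.167; power about 17%.

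A by-arm table can therefore only describe.

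**The case against.** **On eligibility.** Reading exclusion 2 so that it empties an arm the protocol sets out to create defeats the protocol's purpose. Several criteria make sense only before surgery, and Section 3.1.1 applies the list to clinic patients being offered the study. This stands as evidence of intent: status before the tether operation is the likely meaning. But there is no other list, Section 3.4.2 makes this one binding, and nothing in the text supplies the anchor.

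**On pooling.** Much prospective capture is chart abstraction too. Events in the early weeks (Section 3.1.3), surgical data (Section 4.2) and the post-surgical data that include the complication form (Section 5.1.2.2) all come from the medical record, and staff also monitor it for AEs (Section 8). This stands and limits the point. A reader might infer that the primary rate is biased, probably downward; the documents do not show that, and the arms may not differ. A reader might also calculate how far the prospective rate could lie from a pooled one. That needs an assumed R and an assumed event count, and its extremes put as many events as possible into one arm, so it does not measure impact.

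**On by-arm results.** They are imprecise, the study is non-comparative, and Section 6.3.2 does not forbid such a table. All true, which is why the request is descriptive only.

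**On stopping rules.** A reader might infer that retrospective patients could use up the first-5 and first-10 looks in Section 6.6. The text points the other way: the consequence of a rule is a halt to enrollment (Section 6.5), and monitoring meetings are keyed to enrolling successive patients. Only a clarification is needed.

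**Conclusion.** The point holds in three parts.

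1. A stated rule fails. Taken literally, exclusion 2 admits none of the retrospective arm, and the age criterion could drop some patients even with an exception. This rests on the wording alone.
2. The primary AE/SAE rate and the Cobb analysis have no planned breakdown by arm, despite a real difference in follow-up from the day of surgery. Any resulting bias is of unknown size and direction and may be small.
3. The enrollment statements conflict: no target, yet 30 over both arms, yet all past patients. The Synopsis alone might be read as 30 prospective subjects plus all past cases, but Section 3.3.2 makes 30 the combined total. Only the split is open, and 30 is not shown to be wrong.

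These should be corrected. They do not invalidate the pooled estimate. The interval widths above depend on assumed splits, since the documents give none.

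**What to change.** 1. State that for retrospective patients every eligibility criterion, including age and prior surgery, is judged as of just before the index tether surgery. State also that patients who fail on that basis are not enrolled, which keeps to the closing rule of Section 3.4.2.
2. Keep the pooled result. Beside it, report the AE/SAE rate, device-related AE incidence with exact 95% intervals, and Cobb change by arm, labeled descriptive.
3. Reconcile the Synopsis (Number Of Subjects) with Section 3.3.2 and give the expected number in each arm.
4. As a minor clarification, say in Sections 6.5 and 6.6 whether retrospective patients count as cases. No threshold is proposed.

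The cost is protocol wording and one extra set of tables. The by-arm intervals will be wide and support no formal comparison between arms; the pooled estimate and its precision are unchanged.
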